1.2 SCHEMATIC OF STUDY DESIGN

An overview of the study design is provided in Figure 1.

Week	Screening	Pre-Baseline	Baseline	Week 1	Week 1	Week 2	Week 6	Week 12	Follow-up (2 Weeks)	Follow-up (6 Weeks)	Early Termination	
Day	D-42 to D-15	Day -14	(Days -3 to -1)	Day 1	Day 7	Day 14	Day 42	Day 84	Week 12 visit + 14 days	Week 12 visit + 42 days		
Visit Window ¹		+/- 3 days			+/- 3 days	+/- 7 days	+/- 7 days	+/- 7 days	+/- 7 days	+/- 7 days		
Assessments	Site Visit	Site Visit	Site Visit	Site Visit	Phone call ²⁰	Site Visit	Site Visit	Site Visit	Site Visit	Site Visit	Site Visit	
KSS ²⁵				x		x	x	x				
ESS or ESS-CHAD 22				x		x	x	x			x	
Sudden Onset of Sleep Questionnaire				x ²	x	x	x	x			x	
PROMIS Sleep Disturbance Short Form 22			х					х				
PROMIS Sleep-Related Impairment Short Form 22			x					x				
PD Biomarker (qEEG, SPV)		x 12		x ^{12,14}		x ¹²		x 12				
Response BM (Eyetracking)		x ¹³						x 13				
Response BM (EEG Tasks)		x ¹³						x ¹³				
Serology ²⁶	x											
Hematology	x		х			х	х	х	x		х	
Blood Chemistry	x ^{27, 28}		x			х	x ²⁸	х	x ²⁸		x	
Coagulation	x		x					x	x		x	
Urinalysis	x		х			х	х	x	x		х	
Drug of abuse/Alcohol test	x		х					x				
Hair sample collection 33			x				x	x		x		
C-SSRS 31	х		x			х	х	х	x	x	х	
Randomization				x								
Dispensing of study medication				x			x					
Return of study medication							x	x			x	
Administration of study medication at clinic ¹⁰												
Digital biomarkers					x ¹⁵						x ¹⁵	
PK Sample				x ^{11,17}		x ^{11,17}	x ^{9,17}	x ^{9,17}			x ¹⁷	
Blood sample for Clinical Genotyping									x ¹⁶			
Entry and exit questions ²²			x					x			х	
RBR - Optional Whole Blood Sample				x ¹⁹				x ¹⁹			x ¹⁹	
Safety serum sample		x ²¹										
Adverse Events							х					

Table 1 Schedule of Activities - 12-Week, Double-Blind, Placebo-Controlled Period and Follow-Up (cont.)

ADOS-2 = Autism Diagnostic Observation Schedule, Second Edition; BAI = Beck Anxiety Inventory; CGI-I = Clinical Global Impression-Improvement Scale; CGI-S = Clinical Global Impression-Severity Scale, CRRI = Caregiver-Reported Routines Inventory; C-SSRS = Columbia-Suicide-Severity Rating Scale; CY-BOCS-ASD = Children's Yale-Brown Obsessive Compulsive Scale Modified for ASD; DET = detection test; ECG = electrocardiogram; eCOA = electronic clinical outcome assessment; EEG = electroencephalogram; ESS = Epworth Sleepiness Scale; ESS-CHAD = Epworth Sleepiness Scale for Children and Adolescents; KSS = Karolinska Sleepiness Scale; GLDH = glutamate dehydrogenase; IDN = identification test; ONB = one back test; PedsQL = Pediatric Quality of Live Inventory; PRAS-ASD = Parent-rated Anxiety Scale for ASD; PROMIS = Patient-Reported Outcomes Measurements Information System; RBR = research biosample repository; RBS-R = Repetitive Behavior Scale-Revised; SARS-Cov-2 = severe acute respiratory syndrome coronavirus 2; SoA = schedule of activities; SPV = saccadic peak velocity; SRS-2 = Social Responsiveness Scale, Second Edition; SSP-2 = Short Sensory Profile-2; Vineland-3 = Vineland Adaptive Behavior Scales, Third Edition; WASI-II = Wechsler Abbreviated Scale of Intelligence, Second Edition.

- 1 See Table 2 for details on visit windows and options for remote eCOA administration.
- 2 Sudden onset of sleep questionnaire should be done prior to the study drug administration on Day 1.
- 3 If participant discontinues or withdraws from the study treatment prematurely all efforts should be done to perform and complete the Early Termination visit.
- Blood pregnancy beta-hCG test for women of childbearing potential at screening. At specified subsequent visits, pregnancy test using urine sample will be used. If the participant receives a negative result on urine test, dosing will be carried out. If the participant receives a positive result on urine test, a confirmation with blood test has to be obtained. Both serum and urine pregnancy tests will be analyzed locally at the study sites and not by the central laboratory.
- 5 Two test sessions of the neurocognitive battery will take place at the pre-baseline visit (see Section 8.1.5.10).
- For details regarding orthostatic changes, see Section 8.2.3. At visits with dosing, vital signs and orthostatic changes will be measured pre-dose and postdose (hourly for 3 hours [approximately +/- 0.5 hours]), or more frequently if clinically warranted in case of an adverse event of somnolence or sudden onset of sleep.
- 7 Height and weight will be recorded. For adults, only weight will be measured at Week 12 or Early Termination visit.
- 8 Predose and at 2 hours (+/- 0.5 hours) postdose on Day 1 and Day 14. All ECGs (12-lead) will be performed in triplicate, 1-2 minutes apart within 5 minutes.
- 9 Predose

10

Table 1 Schedule of Activities - 12-Week, Double-Blind, Placebo-Controlled Period and Follow-Up (cont.)

- **Day 1**: 2 hours (+/- 0.5 hours), 4 hours (+/- 0.5 hours), and 6 hours (+0.5 hours) postdose, all on the same day; the last sample can be done on site or at home. All Day 1 samples are mandatory for adolescents until the 2nd Internal Monitoring Committee (IMC) + Scientific Oversight Committee (SOC) review. Day 1: only 2 hours (+/- 0.5 hours) postdose is mandatory for high- and low-functioning adult participants.
 - **Day 14**: Predose and at 2 hours (+/- 0.5 hours), 4 hours (end of visit but at least 4 hours postdose), and 6 hours (6-8 hours) postdose; the last sample can be done on site or at home, either on the same day or at a later day within the same timeframe. Day 14: 6 hours (6-8 hours) postdose sample is optional for low-functioning adult participants.
 - PK and safety samples will preferably be taken at the site; however, home nursing services will be available to allow for flexibility in the schedule of visits and to shorten site visits when the visit length depends on blood sampling.
- 12 PD biomarker assessments at time of the day +/- 1 hour of the t_{max} (i.e., approximately 3 to 4 hours postdose [time window: 2.5 to 4.5 hours postdose]) at Pre-Baseline, Day 1, Week 2 and Week 12 visits (for resting state qEEG) and at Pre-baseline, Day 1, and Week 2 visits for saccadic peak velocity [SPV], measured by means of electrooculography [EOG] (SPV is not to be assessed at Week 12).
 - At pre-baseline visit (no dosing), these assessments should be conducted at about the same time of the day (+/- 1 hour) corresponding to t_{max}, (i.e., approximately 3 to 4 hours postdose at dosing days); The duration is approximately ~15 min assessment time + 30 minutes of EEG preparation time.
- Eye-tracking and EEG tasks to take place at the time of the day +/-1h of the t_{max} (i.e., approximately 3 to 4 hours postdose [time window: 2.5 to 4.5 hours postdose]) at Week 12. At pre-baseline visit (no dosing), these assessments should be conducted at about the same time of the day (+/- 1h) corresponding to t_{max}, (i.e., approximately 3 to 4 hours postdose at dosing days). The duration is approximately 50 min assessment time. The tasks will be performed immediately after the PD Biomarker assessments (see footnote 12) using the same equipment and therefore no extra EEG preparation time is needed.
- Additional pretreatment PD biomarker assessment on Day 1 (schedule as described in footnote 12). It is not necessary to remove the EEG electrodes after the pretreatment assessment and therefore the EEG preparation time for the 2nd assessment around t_{max}, (i.e., approximately 3-4 hours postdose; see Footnote 12) will be considerably shorter.
- 15 See Table 3 for details on the digital biomarker SoA.
- 16 Clinical genotyping sample to be drawn once from every participant at any convenient time between Day 1 and the last visit. Leftover from mandatory genotyping samples will be used for RBR if participant consents to RBR.
- 17 Leftover from mandatory PK plasma samples will be used for RBR if participant consents to RBR.
- 19 Whole blood sample will be taken if participant consents to RBR on Day 1 predose and at Week 12 or Early Termination visit.
- 20 Telephone interview to assess for any clinically significant symptoms and/or new medication.
- 21 The serum safety sample can be collected any time for specific assay (e.g., GLDH in case of Liver enzymes) if deemed appropriate by the Investigator for the safety evaluation.
- 22 Refer to Table 9 for further details on the applicable versions of scales to be used according to the age cohort.

Table 1 Schedule of Activities - 12-Week, Double-Blind, Placebo-Controlled Period and Follow-Up (cont.)

- One of the tests in the neurocognitive battery (International Shopping List [ISL] Test 24h delayed condition) will be performed at 24 hours after the initial tests; it will be conducted at the site if the visit is split into 2 days (see Table 2) or over the phone if the participant returned home after the first day. Whenever possible the same test supervisor should perform the initial test and call the participant approximately 24 hours later. Additional questions on duration and quality of sleep will be asked.
- 24 At visits with dosing, the attention tasks of the neurocognitive battery (DET, IDN, and ONB) will be repeated 3-4 hours post dose.
- 25 At visits with dosing, the KSS will be done pre-dose and 3-4 hours post dose.
- 26 At the discretion of the Investigator and Sponsor, participants could be tested for SARS-CoV-2 at screening and at any time during the study.
- 27 Blood chemistry at screening includes estradiol and FSH (both for female participants only).
- 28 TSH, free T4, and HbA1c will be assessed at screening, Week 6, and at the 2-week follow-up.
- 30 Correct version will be predefined on eCOA device: "At baseline" version to be used at pre-baseline and baseline visits; "Since Last Visit" version to be used subsequently.
- 31 Correct version will be predefined on eCOA device: "At baseline" version to be used at screening visit; "Since Last Visit" version to be used subsequently.
- 32 The ability to provide informed consent will be evaluated for each participant by the Principal Investigator using their clinical judgment.
- Hair samples are collected from the study participants who have sufficient hair only (assessed at each collection timepoint). In addition, optional hair samples are collected from the support persons (if consent is given in the applicable Informed Consent Form). All hair strands should be at least 1 cm long.

Table 2 Visit Scheduling Details

Week	Screening	Pre-Baseline	Baseline	Week 1	Week 1	Week 2	Week 6	Week 12	Follow-up (2 Weeks)	Follow-up (6 Weeks)	Early Termination
Day	D-42 to D-15	Day -14	Days -3 to -1	Day 1	Day 7	Day 14	Day 42	Day 84	Week 12 visit + 14 days	Week 12 visit + 42 days	
Visit Window		+/- 3 days			+/- 3 days	+/- 7 days	+/- 7 days	+/- 7 days	+/- 7 days	+/- 7 days	8-day window
On-site assessments	May be split up into two visits within a 7-day window (but up to a 15-day window in case of unexpected delays due to logistical or technical reasons).	May be split into two visits within visit time window.	May be split into two visits within visit time window.	Visit cannot be split.	N/A	Visit cannot be split.	May be split into two visits within visit time window.	May be split into two consecutive days.	May be split into two visits within visit time window.	May be split into two visits within visit time window.	May be split into two visits within visit time window.
Remote eCOA assessments	May be done at any day within visit time window.	May be done at any day within visit time window.	May be done at any day within visit time window.			May be done at any day within visit time window.	May be done at any day within visit time window.	May be done on any day prior to the last on-site assessment within the visit window	May be done at any day within visit time window.	May be done at any day within visit time window.	May be done at any day within visit time window.

Table 3 Digital Biomarker Schedule of Activities

	Screening	Pre- baseline	Baseline	Week 1	Week 1	Week 2	Week 6	Week 12	Follow Up (2 Weeks)	Follow Up (6 Weeks)	Early Termination ^a
	D-42		D-3						Week 12 visit	Week 12 visit	
Day	to D-15	D-14	to D-1	Day 1	Day 7	Day 14	Day 42	Day 84	+14 days	+42 days	
Visit window		+/- 3 days			+/- 3 days	+/- 7 days	+/- 7 days	+/- 7 days	+/- 7 days	+/- 7 days	
Assessments	Site Visit	Site Visit	Site Visit	Site Visit	Phone Call	Site Visit	Site Visit	Site Visit	Site Visit	Site Visit	Site Visit
Identification of targeted behaviors for app		х									
Hand over technology and training		х									
Completion of In- Clinic Assessments		х	Х	(d		х	х	Х			
Completion of At- Home Assessments ^e					X						
Review of compliance ^b				X	Х	х	x				
Return of technology and completion of satisfaction survey ^c								×			х

- a. If participant discontinues or withdraws from the study treatment prematurely all efforts should be done to perform and complete the Early Termination visit.
- b. Participants with inadequate compliance will be re-encouraged to use the digital biomarker technology. If technical problems are identified devices may be exchanged or guidance will be given how to correctly use the technology.
- c. Final satisfaction surveys on the participant's experience about collection of digital biomarker data will be completed by participants and by support persons on the tablet computers used for the electronic clinical outcome (eCOA) assessments.
- d. Completion of in-clinic assessments can be done either at baseline or on Day 1.
- e. At-home active tests will be done once a week.

Table 4 Schedule of Use of Technology for Digital Biomarkers

Activity type	Activity description	Duration	Frequency
	EQ-5D-5L	2 minutes	Monthly
Smartphone data collected through user interaction (Active Tasks) ^a	Three tasks that capture data relevant to core and associated symptoms of ASD	5 minutes	Weekly
	Recording of a conversation between the support person and study participant	5 minutes	Weekly
Data collected without user interaction (Passive Monitoring)	Body movement, location, sleep and physiological recording	Continuous	Daily

a *Three* Active Tasks should be completed each *week* by the study participant. In addition, the support person should record a conversation with the study participant at least once per week and complete a numerical response scale to evaluate conversation quality. Active Tasks can be performed at days and times which the study participant and/or support person deem convenient. Study participants are strongly encouraged to *choose a regular day each week to complete all tasks*, adhere to this schedule and collect as much data as they are able to. If participants find the schedule too burdensome, they may choose to reduce the assessment frequency without violating the protocol.

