8.5 PHARMACOKINETICS

Blood samples for the determination of plasma concentrations of RO7017773 will be collected as outlined in the SoA (see Section 1.3. *Note: On visits Day 1 and Day 14, the study drug should be taken with breakfast or some food such that t_{max} is reached after approximately 2 hours). Following review of the second interim analysis, sampling on Day 1 may be reduced for adolescents to be similar to that for high- and low-functioning adults. This will be confirmed as part of the IMC + SOC review of PK data from adolescents. Plasma RO7017773 concentrations will be measured by a specific and validated LC-MS/MS method. Topical application of local anesthetic is permitted if necessary for blood sampling. Home nursing services may be provided, if feasible to collect blood samples at the participant's household.*

If required, remaining PK samples may also be used for assay development/validation (e.g., for metabolites and measurement of exploratory biomarkers).

The PK samples will be destroyed within 2 years after the date of final CSR. Details on sampling procedures, sample storage and shipment are given in the Sample Handling Manual.

For participants who consent to RBR, leftover samples will be transferred to RBR (see Section 8.9).

Drug concentration information that would unblind the study, will not be reported to investigative sites or blinded personnel until the study has been unblinded.

Any changes in the timing or addition of timepoints for any planned study assessments must be documented and approved by the relevant study team member and archived in the Sponsor and site study files. This will not constitute a protocol amendment. The IRB/IEC will be informed of any safety issues that require alteration of the safety monitoring scheme or amendment of the ICF.

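### Table 1 schedules EEG and SPV around a t_max of 3 to 4 h postdose, but Section 8.5 puts t_max at about 2 h for the same Day 1 and Day 14 doses

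*Protocol*

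**What the plan says.** **PD biomarkers (resting EEG, SPV).** Protocol Section 1.3, Table 1, footnote 12 sets the recordings within plus or minus "1 hour of the t_{max} (i.e., approximately 3 to 4 hours postdose [time window: 2.5 to 4.5 hours postdose". It covers resting EEG on Day 1 and at Weeks 2 and 12, and SPV on Day 1 and at Week 2. The pre-baseline recording is matched to the same clock time. Footnote 14 repeats the equation for Day 1: "2nd assessment around t_{max}, (i.e., approximately 3-4 hours postdose; see Footnote 12".

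**Response biomarkers.** Footnote 13 uses the same anchor: "Eye-tracking and EEG tasks to take place at the time of the day +/-1h of the t_{max} (i.e., approximately 3 to 4 hours postdose". The only postdose visit for these is Week 12.

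**Pharmacokinetics.** Section 8.5 asks for dosing with food at the Day 1 and Day 14 visits and gives the aim: "such that t_{max} is reached after approximately 2 hours".

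**ECG.** Footnote 8 times the postdose ECG accordingly: "Predose and at 2 hours (+/- 0.5 hours) postdose on Day 1 and Day 14".

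**Analysis.** SAP Section 3 drops a post-treatment EEG only when the last dose was more than 6 h before it. SAP Section 4.5.3 compares beta power with placebo at each postdose recording by two-sided t-test, with a threshold of p < 0.1. It makes no reference to time since dose.

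**The concern.** Day 1 and Day 14 (Week 2) are both PD biomarker visits and the two visits to which Section 8.5 applies its t_max. The ECG and PK text works from about 2 h; the EEG and SPV footnotes work from 3 to 4 h. Both are presented as the peak after one and the same dose.

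At stake is what the PD readout can be said to show. Protocol Section 4.2.3.1 uses these biomarkers to quantify the strength of the drug effect in the brain. A reader who takes the footnote at its word will place the EEG effect at peak plasma exposure, and will assume that the ECG and the EEG describe the same exposure.

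The PK sampling often cannot settle the matter. For adults only the 2-h sample is mandatory on Day 1, and Week 12 sampling is predose only. The SAP's 6-h rule does not restore the link to t_max either: a recording at 5.5 h would count in full.

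**Working it through.** **Inputs**
- Footnote 12: rule t_max ± 1 h; target 3 to 4 h; allowed window 2.5 to 4.5 h (length 2.0 h).
- Section 8.5: t_max about 2 h on Day 1 and Day 14, with food.
- Footnote 8: ECG at 2 ± 0.5 h, that is 1.5 to 2.5 h.
- Section 8.3.7.1: half-life below roughly 20 h. No other half-life is visible.

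**1. Reproduce the plan's window.** Band = (t_max − 1, t_max + 1).
- t_max 3.0 h gives 2.0 to 4.0 h.
- t_max 3.5 h gives 2.5 to 4.5 h, which matches.
- t_max 4.0 h gives 3.0 to 5.0 h.

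The stated window follows only from t_max = 3.5 h, the midpoint of 3 to 4 h.

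**2. Apply the same rule to Section 8.5.** t_max 2 h gives 1.0 to 3.0 h. The overlap with 2.5 to 4.5 h is 3.0 − 2.5 = 0.5 h, and 0.5 / 2.0 = 25%. So 75% of the stated window lies outside the band. The 3 to 4 h target meets the band only at 3.0 h, and the 2-h point is itself outside the window.

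**3. Allow for the word approximately (assumed range for t_max).**

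| t_max (h) | ±1 h band (h) | Overlap (h) | Share of window outside |
|---|---|---|---|
| 1.5 | 0.5–2.5 | 0 | 100% |
| 1.75 | 0.75–2.75 | 0.25 | 87.5% |
| 2.0 | 1.0–3.0 | 0.5 | 75% |
| 2.25 | 1.25–3.25 | 0.75 | 62.5% |
| 2.5 | 1.5–3.5 | 1.0 | 50% |

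More than half of the window is outside for any t_max below 2.5 h.

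**4. ECG against EEG.** The windows 1.5 to 2.5 h and 2.5 to 4.5 h share only the 2.5-h boundary.

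**5. How much exposure is lost.** Assume mono-exponential decline from 2 h: C(t)/C(2) = exp(−ln 2 × (t − 2) / half-life).

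| Assumed half-life (h) | 3.5 h | 4.5 h |
|---|---|---|
| 20 | 0.949 | 0.917 |
| 12 | 0.917 | 0.866 |
| 8 | 0.878 | 0.805 |

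An alternative is a one-compartment oral model with its peak fixed at 2 h. It gives 0.965 and 0.932 of C_max at 3.5 and 4.5 h for a 20-h half-life, 0.895 and 0.791 for 5 h, and 0.859 and 0.715 for 3 h. Both models are illustrations, because the documents bound the half-life only from above.

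**The case against.** The best defence is that this is a labelling mismatch with little consequence. Much of it stands.

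- **Planned reporting.** A reader might infer that a null EEG result will be reported as showing no effect at C_max. No section plans that. The endpoints in protocol Table 6 speak of pre- to post-dosing, SAP 4.5.3 of postdose recordings, and the 6-h rule is not a t_max rule. The SAP section visible here analyses resting beta power only.
- **Sleepiness and attention.** It is tempting to extend the point to the KSS and attention tasks, since "the KSS will be done pre-dose and 3-4 hours post dose". Footnotes 24 and 25 never refer to t_max, so they do not contradict Section 8.5.
- **Week 12.** Section 8.5 gives the food instruction and the 2-h figure for Day 1 and Day 14 only. Footnote 10, on dosing at the clinic, is blank in the available copy. A conflict for the Week 12 EEG, or for footnote 13's eye-tracking and EEG tasks, is therefore inference. SAP 4.5.3 also calls the Week 2 EEG optional, which may leave Day 1 as the main directly affected EEG.
- **Feasibility.** A reader might conclude that sites cannot comply. They can: the explicit 2.5 to 4.5 h bracket is workable alongside a 2-h ECG.
- **Size.** The expected exposure loss is small under most assumed half-lives, and nothing says that the EEG effect peaks when plasma does.
- **Partial cover.** PK draws at 4 h exist for some participants, and SAP 4.5.2 plans population PK and leaves exposure–PD correlations to a post hoc decision.

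A delayed PD peak does not rescue the text. No section states one, and the footnotes tie the timing to t_max. If a lag was intended, the t_max wording still needs correcting.

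**Conclusion.** The contradiction is real and sits in current text. For the Day 1 and Day 14 doses, footnotes 12 and 14 place t_max at 3 to 4 h and Section 8.5 at about 2 h. Under the footnote's own ±1 h rule, 75% of its window lies outside the band implied by Section 8.5. The share varies from 50 to 100% if t_max is taken anywhere from 2.5 down to 1.5 h.

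The consequence is a mis-anchored window and a probably modest dilution of exposure: about 88 to 95% of the 2-h concentration at 3.5 h, assuming mono-exponential decline and half-lives of 8 to 20 h. It does not invalidate the EEG or SPV endpoints. They are exploratory, and the primary endpoint and sample size are unaffected.

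A reader might go further and say that the recordings miss the drug's peak effect. The documents do not support that, because they give a plasma peak and no time for the PD peak. They also do not show which of the two t_max figures is right.

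**What to change.** **Protocol.** Reconcile footnotes 12 and 14 with Section 8.5 so that one t_max applies to Day 1 and Day 14, with the matching pre-baseline clock time. Check footnote 13, and state what holds at Week 12. If 3 to 4 h is deliberate, give the reason, remove the t_max ± 1 h description, and do not interpret the EEG and SPV results as effects at peak exposure.

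**SAP 4.5.3.** Summarise actual time from dose to each postdose EEG by arm and visit. Add a supportive beta-power contrast that accounts for time since dose, for example as a covariate in a linear model alongside the planned t-tests. Letting the slope differ by arm would show whether the drug effect varies with time; a common slope only adjusts for timing imbalance. Do not restrict the analysis to recordings within 1 h of a 2-h t_max: sites following the schedule would contribute only recordings between 2.5 and 3.0 h, a sparse and self-selected subset of about 28 to 35 participants per arm.

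**Cost.** Footnote wording, one summary table and one supportive model. The SAP describes conduct largely in the past tense, so participants already recorded keep the 2.5 to 4.5 h timing. For them the remedy is analytical, and with arms of this size the time-adjusted estimate will be imprecise.
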